6.2.2 DC Phase Subjects

DC phase subjects will undergo the identical procedures, and in addition will undergo a screening ophthalmologic examination to consist of visual acuity determination, biomicroscopy, and dilated fundoscopy; and testing for MSFC, FSS, and SF-36.

6.3 Treatment Period (Cycle 1) – Days 8, 15 and 22 (± 1) – All Subjects

All DE and DC phase subjects will be admitted to the unit the morning of dosing for a brief physical examination (including neurological examination and EDSS where clinically indicated), and vital signs, ECG, weight (Day 22 only) and pregnancy testing if applicable (Day 22 only). Any adverse events and concomitant medications taken since the last visit will be recorded and eligibility confirmed.

An indwelling intravenous cannula will be sited in a forearm. A pre-dose blood sample will be taken for safety samples, PD and immune parameter analysis.

Study drug will be administered at the scheduled time by a slow intravenous infusion over 10 minutes. Subjects will be closely monitored for changes in their health or physiological status. At any time during dosing, the infusion rate can be reduced or turned off in response to an adverse event occurring. Once the infusion is completed, the cannula will be flushed with 0.9% sodium chloride for injection. The cannula will stay *in situ* until discharge.

Subjects will be required to remain in bed for four hours post dose and then will be allowed to mobilise gently around the unit.

Vital signs will be repeated mid-way through the infusion (5mins), 15 and 30 minutes, 2 and 4 hours post-dose. ECGs will be repeated 30 minutes, 1, 2 and 4 hours post-dose. Adverse event enquiry will be completed mid-way through the infusion, 15 and 30 minutes post dose and ongoing throughout the inpatient stay.

Meals, snacks and drinks will be provided throughout the day.

Subjects will be discharged mid afternoon but may remain in the unit for up to 24 hours at the discretion of the Investigator.

Subjects will return the following morning for a 24-hour post-dose blood sample for PD and immune parameter blood sampling.

6.4 Treatment Period (Cycles 2 – 3) – Days 1, 8, 15 and 22 (+ 1) – DC Phase Subjects Only

DC phase subjects will be admitted to the unit the morning of dosing for a brief physical examination (Day 1 only), weight (Day 1 and Day 22), ECG and vital signs. Any adverse events and concomitant medications taken since the last visit will be recorded and eligibility confirmed. An MSFC, FSS, and EDSS will be performed on Day 1 of each cycle, and the SF-36 will be performed at the end of Cycle 3 only. An ophthalmologic examination, to consist of visual acuity determination, biomicroscopy, and dilated fundoscopy, will be performed within a week of the end of Cycle 3. (EDSS will be repeated following neurological examination at any visit where indicated by a change in functional status).

A cranial MRI will be performed at the end of Cycle 3 (details to be provided in the companion Radiology Manual of Operations).

An indwelling intravenous cannula will be sited in a forearm. A pre-dose blood sample will be taken for safety samples (Days 8 and 22 in Cycles 2 and 3, and End of Dosing or Early Discontinuation where applicable). A pre-dose blood sample for PD and immune parameter analysis will be taken on Day 22 of each cycle.

Version 5

Study drug will be drawn up and administered at the scheduled time by a slow intravenous infusion over 10 minutes. Subjects will be closely monitored for changes in their health or physiological status. At any time during dosing, the infusion rate can be reduced or turned off in response to an adverse event occurring. Once the infusion is completed, the cannula will be flushed with 0.9% sodium chloride for injection. The cannula will stay *in situ* until discharge.

Subjects will be required to remain in bed for four hours post dose and then will be allowed to mobilise gently around the unit.

Vital signs will be repeated mid-way through the infusion (5 mins), 15 and 30 minutes, 2 and 4 hours post-dose. ECG will be repeated at 4 hours post-dose. Adverse event enquiry will be completed mid-way through the infusion, 15 and 30 minutes post dose and ongoing throughout the inpatient stay.

Meals, snacks and drinks will be provided throughout the day.

Subjects will be discharged mid afternoon but may remain in the unit for up to 24 hours at the discretion of the Investigator.

6.5 Treatment Period -End of Dosing (Day 29) or Early Discharge-(7 +1 days following last dose of drug)

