6.1 Screening (Days -28 to -2)

Subjects who are willing to participate in the study and who have signed a Consent Form will be screened for eligibility within 28 days of dosing.

Screening tests will include a record of medical history, a physical examination (excluding breast, genital or rectal examination, unless clinically indicated), vital signs, weight, height, ECG, safety laboratory tests (haematology, biochemistry, pregnancy test and/or FSH where applicable, hepatitis B, C and HIV serology, urinalysis) and drug of abuse screen. An Expanded Disability Status Scale will be completed (see Section 9.4). A cranial MRI scan will be performed during the screening period.

Subjects who meet all of the inclusion criteria and none of the exclusion criteria will be accepted onto the study.

Documentation of the subject's fulfillment of the entry criteria, whether eligible or not, is to be completed by the investigator.

6.2 Treatment Period (Cycle 1) – Day 1

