6.2.1 DE Phase Subjects

DE phase subjects will be admitted to the unit for pre-study safety blood, PD and immune parameter analysis and urine testing, pregnancy testing (if applicable), weight, vital signs, ECG and EDSS on Day 1

Subjects will undergo a physical examination (including neurological) and vital signs. Any medical history and concomitant medications taken since screening will be recorded and eligibility confirmed.

An indwelling intravenous cannula will be sited in a forearm.

A light breakfast will be consumed approximately 30 minutes prior to the scheduled dosing time.

Study drug will be drawn up in accordance with instructions in the Operations Manual and administered at the scheduled time by a slow intravenous infusion over 10 minutes. Subjects will be closely monitored for changes in their health or physiological status. At any time during dosing, the infusion rate can be reduced or the infusion turned off in response to an adverse event occurring. Once the infusion is completed, the cannula will be flushed with 0.9% sodium chloride for injection. The cannula will stay *in situ* until discharge on Day 2.

Subjects will be required to remain in bed for four hours post dose and then will be allowed to mobilise gently around the unit.

Vital signs will be repeated mid-way through the infusion (5 mins), 15 and 30 minutes, 2,4, 6, 8, 10, 12, 16, 20 and 24 hours post-dose. ECGs will be repeated 30 minutes, 1, 2, 4, 6, 8, 12 and 24 hours post-dose. Adverse event enquiry will be completed mid-way through the infusion (5 mins), 15 and 30 minutes, 2, 4, 6, 8, 10, 12, 16, 20 and 24 hours post dose and ongoing throughout the inpatient stay.

Meals, snacks and drinks will be provided throughout the day and subjects will remain overnight on the unit.

A 24-hour post-dose blood sample for PD and immune parameter sampling will be obtained the morning of Day 2 by venesection (**not via the indwelling cannula**). The cannula can be removed and the subject discharged from the unit if well.

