creatinine, follicle stimulating hormone [FSH; at pre-study for postmenopausal women only]), and urinalysis (pH, specific gravity, protein, glucose, ketones, white blood cells, red blood cells, leucocyte esterase, urobilinogen, bilirubin, culture where applicable) pre-study, prior to the first dose, weekly, at End of Dosing, and at Follow-Up. Serology for Hepatitis B, C and HIV and urine drug of abuse at screening only.

⁷ Performed pre-study, pre-dose and 30 minutes, 1, 2, 4 hours (and 6, 8, 12 and 24 hours on Day 1) post-dose, at end of study dosing, and at follow-up.

⁸ Screening (serum); otherwise, urine dipstix, confirmed with serum hCG if equivocal.

⁹ EDSS will be assessed at Screening, Baseline, End of Dosing and at other timepoints when clinically indicated by neurological examination

¹⁰ 3 x 10 mL whole blood sample collected pre-each dose

¹¹ 3 x 10 mL whole blood sample collected 24 hours post each dose

Version 5

| | Pre- | Clinic Visit (Cycle 1) | | | | | | | | | |
|--|----------------|------------------------|-----|----------------|---|----------------|----|----------------|----|------------------|--|
| | Study | | Day | | | | | | | | |
| | (-28 | 1 | 2 | 8 | 9 | 15 | 16 | 22 | 23 | Early Discharge: | |
| Study Procedures | days) | Baseline | | + 1 day | | + 1 day | | + 1 day | | All Subjects | |
| Medical history | Х | | | | | | | | | | |
| Physical examination | X ¹ | X ^{2,3} | | X ² | | X ² | | X ² | | X ¹ | |
| Neurological examination ⁴ | x | X ³ | | | | | | | | x | |
| Ophthalmologic examination ⁵ | x | | | | | | | | | x | |
| Inclusion/ exclusion criteria | х | | | | | | | | | | |
| Informed consent | Х | | | | | | | | | | |
| Body weight | Х | X ³ | | | | | | Х | | Х | |
| Vital signs ⁶ | Х | Х | | Х | | Х | | Х | | X | |
| Clinical laboratory testing ⁷ | x | X ³ | | х | | х | | х | | х | |

Table 3 Schedule of Events (DC Phase – Cycle 1)

¹ Thorough examination pre-study and at end of study dosing.

² Symptom-directed examination weekly during the first cycle, once each subsequent cycle, and at follow-up.

³ If pre-study assessment was performed within 3 days prior to baseline, assessments do not need to be repeated prior to initiation of dosing.

⁴ Neurological examination will be conducted at screening, baseline and end of dosing, and at other timepoints when indicated by history and adverse events.

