⁵ Visual acuity determination, biomicroscopy, and dilated fundoscopy during screening and within a week of the Early Discharge.

⁶ Temperature, pulse, respiration, blood pressure pre-study; prior to dosing, midway through (5 minutes), and 15 and 30 minutes, 2 and 4 hours (and 6, 8, 10, 12, 16, 20 and 24 hours post-dose on Day 1) post-dosing at each clinic visit, and at follow-up.

⁷ Hematology (red blood cell [RBC] count, hemoglobin, hematocrit, mean corpuscular volume [MCV], mean cell haemoglobin concentration [MCHC], platelet count, white blood cell [WBC] count, differential cell count [absolute and percentage; neutrophils, lymphocytes, monocytes, eosinophils, basophils], and reticulocyte count [absolute and percentage], coagulation (prothrombin time [PT], partial thromboplastin time [PTT], INR), serum chemistry (conjugated bilirubin, alanine aminotransferase [ALT], aspartate aminotransferase [AST], alkaline phosphatase, lactate dehydrogenase [LDH], gamma-glutamyltransferase (GGT), amylase, lipase, total protein, albumin, globulin, sodium, potassium, chloride, bicarbonate, calcium, adjusted calcium, magnesium, phosphate, glucose, urea, creatinine, , follicle stimulating hormone [FSH; at pre-study for postmenopausal women only]), and

Version 5

| | Pre- | | | Clinic Visit (Cycle 1) | | | | | | |
|-----------------------------|-------|-----------------|-----------------|------------------------|-----------------|----------------|-----------------|----------------|-----------------|------------------|
| | Study | | Day | | | | | | | |
| | (-28 | 1 | 2 | 8 | 9 | 15 | 16 | 22 | 23 | Early Discharge: |
| Study Procedures | days) | Baseline | | + 1 day | | + 1 day | | + 1 day | | All Subjects |
| ECG ⁸ | Х | Х | | Х | | Х | | Х | | Х |
| Echocardiogram | Х | | | | | | | | | |
| Pregnancy test ⁹ | Х | | | | | | | Х | | Х |
| EDSS ¹⁰ | Х | Х | | | | | | | | Х |
| MSFC | | Х | | | | | | | | Х |
| FSS | | Х | | | | | | | | Х |
| SF-36 | | Х | | | | | | | | Х |
| Cranial MRI | Х | | | | | | | | | Х |
| Concomitant | х | х | | х | | х | | х | х | х |
| medications | ^ | ^ | | ^ | | ^ | | ^ | ^ | ^ |
| Adverse events | | Х | | Х | | Х | | Х | | Х |
| Study Drug | | x | | x | | x | | x | | |
| Administration | | ~ | | ~ | | ^ | | ^ | | |
| PD & Immune | | | | | | | | | | |
| parameter sampling | | X ¹¹ | | X ⁹ | | X ⁹ | | X ⁹ | | |
| Pre-each dose | | | | | | | | | | |
| PD & Immune | | | | | | | | | | |

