| parameter sampling | | | X ¹² | | X ¹⁰ | | X ¹⁰ | | X ¹⁰ | |
| 24hrs Post-each dose | | | | | | | | | | |

urinalysis (pH, specific gravity, protein, glucose, ketones, white blood cells, red blood cells, leucocyte esterase, urobilinogen, bilirubin, culture where applicable) pre-study, prior to the first dose, weekly during Cycle 1, at End of Dosing, and at Follow-Up (all subjects). For DC phase subjects only, Days 8 and 22 during Cycles 2 and 3 and at the end of Cycles 4 and 6. Serology for Hepatitis B, C and HIV and urine drug of abuse at screening only.

⁸ Performed pre-study, pre-dose and 30 minutes, 1, 2, 4 hours (and 6, 8, 12 and 24 hours on Day 1) post-dose, at end of study dosing, and at follow-up.

⁹ Screening (serum); otherwise, urine dipstix, confirmed with serum hCG if equivocal.

¹⁰ EDSS will be assessed at Screening, Baseline, Early Discharge and at other timepoints when clinically indicated by neurological examination

¹¹ 3 x 10 mL whole blood sample collected pre-each dose

¹² 3 x 10 mL whole blood sample collected 24 hours post each dose

Version 5

Table 4 Schedule of Events (DC Phase – Cycles 2-3)

| | Clinic Visit (Cycles 2-3) | | | | | | | | | |
|---|---------------------------|--------------|----------------------|----------------------|--|--|--|--|--|--|
| | | Days (ea | ch cycle) | | | | | | | |
| Study Procedures | 1 + 1 day | 8 + 1 day | 15 + 1 day | 22 + 1 day | End of Study Dosing or Early Discharge: All Subjects | Follow-Up (15 +2 Days Post-End of Dosing): All Subjects | | | | |
| Physical examination | X ¹³ | | | | X ¹ | Х | | | | |
| Neurological examination ¹⁴ | Х | | | | Х | | | | | |
| Ophthalmologic examination ¹⁵ | | | | | х | | | | | |
| Body weight | | | | | Х | Х | | | | |
| Vital signs ¹⁶ | Х | Х | Х | Х | Х | Х | | | | |
| Clinical laboratory testing ¹⁷ | | Х | | Х | Х | Х | | | | |
| ECG ¹⁸ | х | х | х | х | х | Х | | | | |
| Pregnancy test ¹⁹ | | | | Х | Х | Х | | | | |

¹³ Symptom-directed examination once each cycle and at follow-up.

¹⁵ Visual acuity determination, biomicroscopy, and dilated fundoscopy within a week of End of Dosing or Early Discharge.

¹⁶ Temperature, pulse, respiration, blood pressure pre-study; prior to, midway through, and 15 and 30 minutes, 2 and 4 hours post-dosing at each clinic visit, and at follow-up.

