7.4 Safety Laboratory Tests

Blood and urine samples will be taken for safety laboratory assessment (haematology, biochemistry, serology and urinalysis) as described in Tables 2, 3 and 4. The tests will be performed at a local laboratory according to their laboratory standard operating procedures. The normal ranges will be supplied to the investigator and sponsor prior to the start of the study. The following tests will be included in each panel:

Version 5

- Haematology: Red blood cells, haemoglobin, haematocrit, mean cell volume, mean cell haemoglobin, mean cell haemoglobin concentration, platelet count, white blood cell count, reticulocytes (absolute and percentage), differential (absolute and percentage): neutrophils, lymphocytes, monocytes, eosinophils, basophils.
- Coagulation: Prothrombin Time (PT), Activated Partial Thromboplastin time (APTT), INR
- Biochemistry: Sodium, potassium, calcium, glucose, albumin, globulin, adjusted calcium, phosphate, bicarbonate, chloride, magnesium, aspartate aminotransferase, alanine aminotransferase, alkaline phosphatase, glutamyl transferase, lactate gammadehydrogenase, conjugated bilirubin, total protein, plasma creatinine, urea, amylase, lipase, follicle stimulating hormone (screening only where applicable), quantitative hCG (where applicable), Urinalysis: Protein, glucose, pH, leucocyte esterase, white blood cells, red blood cells, ketones, urobilinogen, , specific gravity, bilirubin, culture (if applicable), qualitative hCG (where applicable)

Urine drug of abuse screen: Opiates, amphetamines, cannabinoids, benzodiazepines, methadone

Serology: Hepatitis B, hepatitis C, HIV

A total of up to approximately 343 mL of blood is required during the DE phase and approximately 506 mL of blood is required during the DC phase with both quantities including PD and immune parameter sampling, per Section 7.7.

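### Table 3 (dose-confirmation Cycle 1) leaves out the Day 1 pregnancy test that Sections 6.2.1 and 6.2.2 require

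*Protocol*

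**What the plan says.** **Text.** The Day 1 list in Section 6.2.1 (DE subjects) includes "urine testing, pregnancy testing (if applicable), weight, vital signs, ECG and EDSS on Day 1". Section 6.2.2 carries that list over: "DC phase subjects will undergo the identical procedures", plus an ophthalmologic examination, MSFC, FSS and SF-36. For the other Cycle 1 visits, Section 6.3 asks of all subjects "pregnancy testing if applicable (Day 22 only").

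**Tables.** Section 6 refers the reader to Table 2 for the DE phase and Table 3 for DC Cycle 1. Their pregnancy-test rows differ at Day 1:

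- Table 2: Pre-Study, Day 1, Day 22, End of Dosing or Early Discharge, Follow-Up.
- Table 3: Pre-Study, Day 22, Early Discharge.

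**Footnotes and related sections.** Footnote 9 to the Table 3 row gives only the type of test: "Screening (serum); otherwise, urine dipstix, confirmed with serum hCG if equivocal". Section 6.1 sets the screening window: subjects "will be screened for eligibility within 28 days of dosing". Section 7.4 lists hCG in its laboratory panels, for example "qualitative hCG (where applicable"), but leaves the timing of samples to Tables 2, 3 and 4.

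**The concern.** Two operative parts of the protocol give different instructions for the visit at which a DC subject is first exposed to the drug. Sites and case report form designers commonly work from the schedule of events, and Section 6 sends them there. If Table 3 is followed as it stands, pregnancy status is not rechecked between screening and Day 22.

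Three features of the protocol make the screening test a weak substitute:

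- Exclusion 14 asks women to agree to contraception while on study drug, so it does not cover the interval between the screening test and the first dose.
- Inclusion 6 requires blood counts, creatinine and transaminases within 3 days before first dose, but no such limit applies to the pregnancy test.
- The DC phase gives up to 12 doses, against 4 in the DE phase, so a weaker pre-dose check in DC has no evident rationale.

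**Working it through.** **1. Is the Day 1 cell really blank?** Table 3 has ten columns: Pre-Study, Days 1, 2, 8, 9, 15, 16, 22, 23, and Early Discharge. The "Pregnancy test" row has ten cells: X, six blanks (Days 1, 2, 8, 9, 15, 16), X (Day 22), blank (Day 23), X (Early Discharge). No cell is missing. The Day 22 mark agrees with Section 6.3, and the ECG, EDSS, MSFC, FSS and SF-36 rows carry their Day 1 marks in the expected column. A text-extraction fault is unlikely.

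**2. Is the blank a waiver?** Footnote 3 gives the only Day 1 exemption: "If pre-study assessment was performed within 3 days prior to baseline, assessments do not need to be repeated prior to initiation of dosing". It is attached to the Day 1 cells for physical examination, neurological examination, body weight and laboratory tests. The pregnancy row has neither a mark nor that footnote at Day 1.

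**3. Does the Day 1 laboratory mark supply the test?** Not clearly. Footnote 7, which itemises the Table 3 laboratory panel, names FSH but not hCG. Pregnancy has a row of its own. The Day 1 laboratory mark is itself subject to footnote 3.

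**4. How old would the last test be at each visit?** The screening window is Days -28 to -2. Counting without a Day 0, which fits the stated limit of 28 days before dosing, the screening test is 2 to 28 days old on Day 1. Age at a later visit = age on Day 1 + (visit day − 1). Days 8, 15 and 22 each have a window of ±1 day.

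| Visit | Table 3 alone, nominal (days) | Table 3 alone, with ±1 | Text, nominal | Text, with ±1 |
|---|---|---|---|---|
| Day 1 dose | 2 to 28 | 2 to 28 | 0 | 0 |
| Day 8 dose | 2+7=9 to 28+7=35 | 8 to 36 | 7 | 6 to 8 |
| Day 15 dose | 2+14=16 to 28+14=42 | 15 to 43 | 14 | 13 to 15 |
| Day 22, next test | 2+21=23 to 28+21=49 | 22 to 50 | 21 | 20 to 22 |

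**5. How many doses?** Days 1, 8 and 15 precede the Day 22 test: 3 of up to 3 × 4 = 12 DC doses.

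**6. Comparison with later cycles.** Table 4 schedules the test on Day 22 of Cycles 2 and 3, so scheduled tests are nominally 28 days apart. Under Table 3 alone, the first gap exceeds 28 days whenever the screening test was done more than 28 − 21 = 7 days before Day 1.

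**The case against.** The best case against the point is that the safeguard is already in the protocol. Section 6.2.1 orders the test, Section 6.2.2 extends it to DC subjects, and eligibility must be confirmed on Day 1, which covers exclusion 13. Nothing in Table 3 says the test is dropped, so harm requires a site to disregard the text. This stands, and it is why the point is minor. It does not remove the contradiction, and confirming eligibility without a test would not detect an early pregnancy.

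Section 6.1 treats the pregnancy test as one of the safety laboratory tests, Section 7.4 lists hCG in the panels, and Table 3 marks laboratory testing on Day 1. This softens the conflict but does not settle it, for the reasons in step 3 of the working.

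The text is not flawless either: under a Day 1 heading, Section 6.2.2 includes an eye examination that Section 7.3 and Table 3 place at screening. One could therefore doubt which source is right. Table 3 has slips of its own, however. Its footnote 7 refers to the end of Cycles 4 and 6 in a phase of three cycles. Table 2 also agrees with the text on Day 1 testing. Treating the table as the part in error is a judgement, but it is the better supported and the safer one.

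Finally, the protocol accepts about 28 days between tests in later cycles, so the shorter end of the 23 to 49 day gap is no worse than its own practice. That is fair. The longer end is not covered, and the doses at issue include the first exposure.

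**Conclusion.** The inconsistency is real. Sections 6.2.1 and 6.2.2 require a Day 1 pregnancy test for DC subjects, where applicable. Table 3 omits it without a waiver.

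For a site using Table 3 alone, the first dose rests on a test 2 to 28 days old instead of a same-day one, and 3 of up to 12 doses precede the next test. These figures assume that there is no Day 0 and that the pregnancy test can fall anywhere in the screening window. The protocol does not say how many of the up to 15 DC subjects would be women needing testing, so the number affected cannot be estimated.

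Severity is low. The right instruction exists in the text, testing from Day 22 onward is scheduled, and nothing in the dose-limiting toxicity rule, endpoints, analysis populations or results depends on it.

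**What to change.** Add an X in the Day 1 cell of the Table 3 pregnancy-test row: pre-dose, where applicable, by urine dipstick as footnote 9 already provides. Table 3 then agrees with Sections 6.2.1 and 6.2.2 and with Table 2. The conflict should not be resolved the other way, by removing the test from the text, because that would leave the first DC dose without a recent check. The cost is one table cell, plus one urine test per applicable subject that the text already requires.

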The nature of the target for MIS416 and the mechanism of action are such that following *in vivo* administration and accumulation of the drug by the reticuloendothelial system, a transient inflammatory response can be expected. Monitoring of patient serum for increased levels of pro-inflammatory cytokines demonstrates the transient nature of MIS416 immunostimulation (Figure 1-6). These findings are very important since they demonstrate that administration of a single bolus of MIS416 does not induce an uncontrolled "cytokine storm", with maximum levels of serum cytokines peaking within 24 hour post delivery, returning to baseline levels by 48 hours.

Analysis of MIS416 - treated patient blood for a sustained inflammatory response, or the occurrence of a "second wave" of inflammatory activity over a longer time period (14 days) demonstrates there is no prolonged inflammatory activity following MIS416

Version 5

dosing. This further demonstrates that MIS416 innate immunostimulation is well controlled *in vivo* (Figure 1-7).

[figure not shown]
Figure 1-6

MIS416 systemic administration induces a transient serum inflammatory cytokine response which peaks within 24 hours following administration. Blood serum was harvested and directly measured for multiple cytokine content using flow cytometry cytokine bead array methodology (Bender MedSystem)

Version 5

Figure 1-7

MIS416 therapy does not lead to the sustained induction or a "second wave "of inflammatory mediators. Peripheral blood serum was harvested from two individual healthy donors and from a patient who had received 1 mg of MIS416 7 days prior to blood sampling. Blood serum was assayed for TNF- α , IL-6 and IL-1 β levels using flow cytometry bead array methodology.

2. Rationale for Study Design

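### Adverse events are actively sought to 24 h after dose 1 but only until discharge after later doses, and the next-morning attendances on Days 9, 16 and 23 are not used to ask about them

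*Protocol*

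**What the plan says.** **Dose 1.** Protocol 6.2.1 states that "subjects will remain overnight on the unit". Adverse-event enquiry is set at mid-infusion, 15 and 30 minutes, and then "2, 4, 6, 8, 10, 12, 16, 20 and 24 hours post dose and ongoing throughout the inpatient stay". Section 6.2.2 extends this to the dose-confirmation (DC) phase: "DC phase subjects will undergo the identical procedures".

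**Doses 2-4 (6.3, both phases).** "Adverse event enquiry will be completed mid-way through the infusion, 15 and 30 minutes post dose and ongoing throughout the inpatient stay". On leaving the unit: "Subjects will be discharged mid afternoon but may remain in the unit for up to 24 hours at the discretion of the Investigator". On the next day: "Subjects will return the following morning for a 24-hour post-dose blood sample for PD and immune parameter blood sampling". At each of these dosing visits, before dosing: "Any adverse events and concomitant medications taken since the last visit will be recorded and eligibility confirmed".

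**Doses 5-12 (6.4, DC phase only).** The wording on enquiry, discharge and recording of events since the last visit is the same. There is no next-morning attendance.

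**Tables 2 and 3.** The adverse-events row is marked on Days 1, 8, 15 and 22 and blank on Days 2, 9, 16 and 23. Concomitant medications are marked on Day 23 but not on Days 2, 9 or 16.

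**Why the first day matters.** Section 1.5 describes "maximum levels of serum cytokines peaking within 24 hour post delivery, returning to baseline levels by 48 hours". Section 7 includes the severity and timing of adverse events in the primary endpoint. Appendix 3 separates grade 3 from grade 4 fever by whether a temperature above 40 °C lasts more than 24 h despite antipyretics, and defines grade 4 rigors by symptoms lasting more than 4 h despite treatment.

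**The concern.** The expected toxicity of this product is an acute post-dose reaction, mainly fever and chills, within the first day. Such reactions are followed by direct enquiry for the whole of that day after dose 1. After later doses, the part of the day that follows discharge is reconstructed from memory at the next dosing visit.

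Two things are at stake:

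- **Quality of the acute data for doses 2-4.** These doses fall in Cycle 1, which is the dose-limiting-toxicity period under 4.4. Fever and rigors are dose-limiting only at grade 4, and that grade turns on measured temperature and elapsed time, which recall a week later supplies poorly. Analysis cannot recover details that were never collected.
- **Reading first against later doses.** Section 2.3 gives the DC phase the job of confirming tolerability over prolonged exposure. If fewer acute reactions are recorded after dose 1, the data cannot separate true adaptation from less complete observation.

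**Working it through.** The plan states no figure on this point, so the check sets the schedules side by side and then bounds the possible effect.

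**1. Scheduled enquiry, by dose**

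| Dose | Named enquiry times | Then | Next-morning attendance | Enquiry scheduled there |
|---|---|---|---|---|
| 1 (6.2.1, 6.2.2) | 12: mid-infusion, 15 and 30 min, 2, 4, 6, 8, 10, 12, 16, 20, 24 h | throughout the overnight stay | in the unit | yes, in the text |
| 2-4 (6.3) | 3: mid-infusion, 15 and 30 min | until discharge | yes, for blood | no |
| 5-12 (6.4) | 3: as above | until discharge | none | not applicable |

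Scheduled 24-h enquiry therefore covers 1 of 4 doses in the dose-escalation (DE) phase and 1 of 12 in the DC phase.

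**2. How events after discharge are collected.** A reaction beginning on the evening of Day 8 is next asked about on Day 15. The same pattern holds for each later dosing visit, and the last dose is followed by the End of Dosing visit about 7 days later. Such events are collected, but by recall.

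**3. Possible size of an artefact.** The inputs below are assumptions; the documents give none of them.

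- p: true probability of an acute reaction (onset within 24 h) per dose, held constant across doses
- f: share of those reactions that begin after discharge
- r: share of those that recall at the next visit recovers
- capture after dose 1 is taken as complete

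Recorded rate after dose 1 = p. Recorded rate after any later dose = p × [1 − f(1 − r)]. The relative fall is f(1 − r), and p cancels.

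| | f = 0.25 | f = 0.50 | f = 0.75 |
|---|---|---|---|
| r = 1.0 | 0% | 0% | 0% |
| r = 0.9 | 2.5% | 5% | 7.5% |
| r = 0.7 | 7.5% | 15% | 22.5% |
| r = 0.5 | 12.5% | 25% | 37.5% |

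For example, with p = 50%, f = 0.50 and r = 0.7, the recorded rate is 0.50 × (1 − 0.50 × 0.30) = 42.5%, against 50% after dose 1. The worst corner is 0.75 × 0.50 = 37.5%, about 38%.

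**4. Shape.** Adverse-event enquiry is worded identically for doses 2-4 and 5-12. The formula gives one step between dose 1 and the rest and no further decline.

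**The case against.** The case against is substantial, and much of it stands.

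- **Events are not lost by design.** Sections 6.3 and 6.4 require events since the last visit to be recorded at every dosing visit, and 7.1 monitors events throughout the study. A reader might infer that acute events must decline with dose number by construction. The documents do not support this: with complete recall the fall is zero, and any fall is a single step.
- **The in-unit window is not simply 4 h.** A reader might take the 4-h vital-signs and bed-rest period as the observation window and conclude that only 4/24 = 17% of the first day is covered. Enquiry runs to discharge, for which no hour is stated, and the investigator may keep a subject for up to 24 h. That discretion helps, but it makes ascertainment uneven rather than complete.
- **Blank table cells prove little alone.** Day 2 is blank too, although 6.2.1 requires a 24-h enquiry. For Days 9, 16 and 23, however, the text and the tables agree in scheduling none.
- **No planned table makes the comparison.** Section 14.5.3.2 tabulates by dose cohort and in total and counts only the first occurrence per subject. All cohorts share the Cycle 1 schedule, so differences between cohorts are not selectively distorted.
- **The cytokine statement does not time symptoms.** A peak within 24 h is compatible with onset before discharge, so f is unknown.
- **Other factors blur the DC comparison.** Dose reduction (4.6) and antipyretic pre-medication (4.7) can also lower later reaction rates, so a common window does not make that comparison clean.

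Closer watching after first exposure is a reasonable choice. None of this explains why subjects already in the unit the next morning are not asked how the night went.

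**Conclusion.** The point holds as a modest one. Active enquiry reaches 24 h after dose 1 but only discharge after later doses, unless a stay is extended. Onset, duration and grade of acute events after doses 2-4 are therefore less reliably captured than they could be at attendances already booked, and acute rates and timing should not be compared directly between dose 1 and later doses.

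Any spurious relative fall is 0-38%, as one step after dose 1. This range assumes complete capture after dose 1, 25-75% of reactions starting after discharge, and 50-100% recovered by recall. The documents support no single value within it. The planned cohort incidence tables and the comparisons between cohorts are not shown to be biased. The change is worth making because it improves primary-endpoint data at almost no cost, not because a planned analysis fails.

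**What to change.** 1. In 6.3 and in Tables 2 and 3, add adverse-event enquiry, concomitant medications and one set of vital signs including temperature at the existing Day 9, 16 and 23 attendances.
2. Mark adverse events on Day 2 in Tables 2 and 3, to match the 24-h enquiry that 6.2.1 already requires.
3. State that any comparison of acute adverse events between the first and later doses uses only an observation window common to the doses compared. After change 1, that can be 24 h within Cycle 1. Once doses 5-12 are included, it can be no longer than the time all subjects spend in the unit.
4. State that doses 5-12 remain limited to in-unit enquiry plus recall.

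**Cost.** A few minutes at each of three visits already scheduled, and slightly more adverse-event entries. Scheduled 24-h enquiry would rise from 1 to 4 of 4 DE doses, and from 1 to 4 of 12 DC doses (1 + 3 = 4). The other 8 DC doses (12 − 4) are not covered, because no next-day attendance exists for them.
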